## **7.3 Conventions**

Continuous variables will be summarized using the number of observations (n), mean, standard deviation (Std Dev), median, minimum, and maximum. The same number of decimal places as in the raw data will be presented when reporting minimum and maximum, 1 more decimal place than in the raw data will be presented when reporting mean and median, and 2 more decimal places than in the raw data will be presented when reporting standard deviation.

Time to event variables will be summarized using Kaplan-Meier (KM) method, which will include the estimated median with 95% CIs and 25th and 75th percentiles.

Unless otherwise specified frequency tabulations will be presented by number and percentage, where the percentage is presented in brackets to 1 decimal place (XX.X%).

P-values, if applicable, will be presented to 3 decimal places. If a p-value is less than 0.05 but is greater than or equal to 0.01, then an asterisk (\*) will be added next to this value. If a p-value is less than 0.01 but is greater than or equal to 0.001, then two asterisks (\*\*) will be

**Avapritinib  
Statistical Analysis Plan Study BLU-285-1303**

added next to this value. Finally, if the p-value is less than 0.001 then three asterisks (\*\*\*) will be added next to this value and it will be presented as <0.001. If the rounded result is a value of 1.000, it will be displayed as >0.999.

Any date information in the listing will use the *date9.* format, for example, 07MAY2002. In the listing, a unit associated with a variable will be presented only once within parentheses either below or next to that variable in the heading portion. If a parameter has multiple units, each unit will be displayed only once, as applicable.

All tables will have their source listing referenced in a footnote. Listings should be sorted by analysis group, patient and visit and have the source data received by data management referenced in a footnote. All tables and listings will be converted into Microsoft Word documents and collated into two complete documents.

An Unknown or Missing category are added to each parameter for which information is not available for 1 or more patients.

Unless otherwise specified, the estimated mean and median for a set of values are printed out to 1 more significant digit than the original values, and standard deviations are printed out to 2 more significant digits than the original values. The minimum and maximum should report the same significant digits as the original values. For example, for systolic blood pressure:

N	XX
Mean (Std Dev)	XXX.X (X.XX)
Median	XXX.X
Min, Max	XXX, XXX

Tabular display of data for medical history, prior/concomitant medications, and all tabular displays of adverse event data are presented by the body system, treatment class, or SOC with the highest occurrence in the avapritinib treatment group in decreasing order, assuming all terms are coded. Within the body system, drug class and SOC, medical history (by preferred term), drugs (by ATC1 code), and adverse events (by preferred term) are displayed in decreasing order. If incidence for more than 1 term is identical, they should then be sorted alphabetically. Missing descriptive statistics or p-values which cannot be estimated are reported as “-”.

The percentage of patients is normally calculated as a proportion of the number of patients assessed in the relevant treatment group (or overall) for the analysis set presented.

For categorical summaries (number and percentage of patients) where a patient can be included in more than one category, describe in a footnote or programming note if the patient is included in the summary statistics for all relevant categories or just 1 category and the criteria for selecting the criteria.

## **7.4 Implementing the Rank-Preserving Structural Failure Time Model**

A conventional analysis of overall survival, taking into account only the randomized treatment arm, does not account for the crossover from regorafenib to avapritinib, and the analysis can be biased and treatment effect underestimated. The rank-preserving structural failure time (RPSFT) model attempts to minimize this bias.

The model assumes that once a patient has switched from regorafenib to avapritinib, the overall survival that would have been seen, had the patient not switched, is multiplied by a given factor once the patient has switched. The observed survival for a patient who has switched is then transformed as if they had never received avapritinib and had continued on regorafenib.

The overall survival for a given patient, can be written as the sum of the time they were off avapritinib + the time they were on avapritinib. Here the time they were off avapritinib is when they were on regorafenib:

$$T_i = T_{\text{offi}} + T_{\text{oni}}$$

The above formulation is also valid for patients randomized to avapritinib ( $T_{\text{offi}} = 0$ ) and those randomized to regorafenib who do not switch ( $T_{\text{oni}} = 0$ ).

The aim of the RPSFT model is to estimate for patients who do switch treatment, the survival time that would have been seen if they had not switched treatment. This adjusted survival time,  $U_i$ , is derived as:

$$U_i = T_{\text{offi}} + T_{\text{oni}}(\exp(\psi)) \quad [1]$$

$\exp(\psi)$ , the acceleration factor, is the factor by which the time on avapritinib is multiplied in order to estimate the time that would have been seen if the patient had not switched.

In applying the model, the first step is to estimate  $\psi$ . This is done by applying formular [1] to all patients. At the correct value of  $\psi$ , an analysis of  $U_i$  by randomized treatment should result in a test statistic of 0. The log rank test will be used for this analysis, and the correct value of  $\psi$  is derived iteratively by running through a search grid in order to find the optimum value.

Once  $\psi$  has been derived, the survival times for patients who switch treatment are then transformed according to [1] above. Note, censoring needs to be applied as appropriate for transformed times that extend further than the data cutoff/end of study.

Once the transformation has been done, the data is then analyzed as usual by an appropriate method.

Further details of the method, and specifically the implementation in SAS, can be found in the PharmaSUG 2018 – Paper EP-04, Implementing the Rank-Preserving Structural Failure Time Model in SAS and R, Bradford J Danner and Indrani Sarkar.

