#### 10.5.3.2.2 Overall Survival

Overall survival is defined as the time from date of randomization to death due to any cause. The primary treatment comparison will be based on a rank preserving structural failure time (RPSFT) model to account for treatment crossover effects from regorafenib to avapritinib. The survival time gained/lost by receiving avapritinib after crossover in the regorafenib group will be estimated. Rank preserving structural failure time reconstructs the survival duration of patients as if they had never received avapritinib, assuming treatment is acting by multiplying survival time by a given factor once a patient starts receiving avapritinib ([Korhonen et al, 2012](#)).

If the patient is alive or the vital status is unknown at the time of analysis, OS will be censored at the date the patient is last known to be alive. The Kaplan-Meier method will be used to estimate the distribution of OS for each treatment group. The HR and its 95% CI will be estimated based on Cox's regression model with stratification factors as covariates.

In addition, the probability of survival by time after randomization based on Kaplan-Meier estimates will be tabulated for each treatment group along with the standard errors estimated by the Greenwood formula.

A gate-keeping method will be implemented to control Type I error. The OS will be analyzed when superiority is demonstrated for both PFS and ORR. The OS will also be analyzed at the follow-up when 264 events (deaths) occur.

A sensitivity analysis will be conducted in the ITT population where treatment crossover is ignored. Other sensitivity analyses may be considered as appropriate.

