**Avapritinib**  
**Statistical Analysis Plan Study BLU-285-1303**

**1.1 Study Design**

This is an open-label, randomized, Phase 3 study in patients with locally advanced unresectable or metastatic GIST previously treated with imatinib and 1 or 2 other tyrosine kinase inhibitors (TKIs).

All study visits are intended to be conducted on an outpatient basis. After provision of written informed consent, patients will be evaluated for study eligibility during the screening period within 4 weeks (28 days) before study drug administration on Cycle 1 Day 1 (C1D1). During the screening period, eligibility will be confirmed; management of baseline concomitant conditions will be recorded and stabilized; baseline symptoms will be assessed; hematology, blood chemistry, mutation status, brain imaging (computed tomography (CT) scan or magnetic resonance imaging (MRI)), and baseline tumor assessments (CT scan or MRI) will be performed.

[figure not shown]
Approximately 460 patients are to be randomly assigned, in a 1:1 ratio, to 1 of 2 treatment arms: Arm A (avapritinib) or Arm B (regorafenib) stratified by TKI treatment (third versus fourth), geographic region (Asia versus rest of the world), and PDGFRA D842V mutation status measured in ctDNA or a tumor sample (PDGFRA D842V mutation present versus absent). PDGFRA D842V mutation present is defined if a PDGFRA D842V mutation is detected per local or/and central testing. At least 70% of the patients enrolled should be receiving the study drug as their third TKI treatment for GIST.

Patients randomized to Arm A will receive avapritinib 300 mg orally (PO) once daily (QD) with the option to escalate to 400 mg PO QD at the Investigator's discretion (the escalation option was removed in protocol amendment 3), if specific criteria are met as described in the protocol. Patients randomized to Arm B will receive regorafenib 160 mg PO QD for 3 weeks out of every 4 week (28 days) cycle (i.e., 3 weeks on/1 week off).

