**1.2.3 Exploratory Objectives**

### **1.3 Sample Size Justification**

The sample size calculation was based upon the assumption that the median PFS for regorafenib is approximately 5 months (Demetri 2013). Assuming avapritinib can reduce the risk of PFS events by 33%, i.e., a hazard ratio (HR) of 0.67 (avapritinib compared to regorafenib), a minimum of 264 PFS events are needed to provide 90% power at a 2-sided alpha of 0.05 for the study. With an 18-month accrual period and a 6-month follow-up period, the total sample size needed for the study is approximately 460 patients (230 patients per arm). This sample size takes a 2% dropout rate into consideration and assumes accrual will follow a truncated exponential distribution with a scaled power parameter of -9.

The sample size calculated for the primary endpoint, PFS, is also sufficient to detect a difference in ORR between the two arms. Assuming a null ORR of 5% and an alternative ORR of 15%, a sample size of 460 patients provides approximately 95% power to detect a difference in ORR using a test of two-proportions at a 2-sided alpha of 0.05.

Assuming the same effect size for OS as PFS (HR = 0.67), the same number of events (264) is required to power the OS analysis. The timing of the OS analysis will occur later than the PFS analysis as it will be at such time when 264 deaths occur.

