##### **4.6.1 Multiplicity**

A gate-keeping method will be implemented to control Type I error. This strategy will apply to the primary and key secondary efficacy endpoints: PFS, ORR, and OS.

PFS will be analyzed first when approximately 264 events are reached. In line with the gate keeping strategy, ORR will only be assessed for superiority should PFS have demonstrated superiority.

A formal OS interim analysis will be performed at the time of the final analysis of PFS and ORR for which superiority is demonstrated. The alpha for the interim analysis of the OS will follow the O'Brien-Fleming boundary method. The amount of alpha spent on OS at the time of the final PFS analysis will be specified according to the actual proportion of deaths observed at the time of the database lock regardless of whether the exact targeted number of PFS events has occurred at the lock. The exact amount of alpha spending at the interim analysis will be calculated using the alpha spending function developed by Lan and DeMet. OS will be analyzed when superiority is demonstrated for both PFS and ORR. The OS will also be analyzed at the follow-up when 264 events (deaths) occur, using the remaining unspent alpha.

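### The re-censoring note in SAP 7.4 cannot take effect when avapritinib prolongs survival, so the crossover-adjusted OS hazard ratio can be modestly biased, in a direction that depends on how crossover relates to prognosis

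*SAP*

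**What the plan says.** SAP 7.4 defines the adjusted survival time as U = T_off + T_on × exp(psi), where T_on is time on avapritinib. Psi is found by applying this formula to all patients and searching a grid for the value at which a log-rank test on U by randomized arm gives zero. No re-censoring is mentioned at that step. After psi has been found, "the survival times for patients who switch treatment are then transformed according to [1] above", and the SAP adds: "Note, censoring needs to be applied as appropriate for transformed times that extend further than the data cutoff/end of study". For SAS implementation it points to an external paper.

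The two documents give the model different roles. Protocol 10.5.3.2.2 says: "The primary treatment comparison will be based on a rank preserving structural failure time (RPSFT) model". SAP 4.6.3.2 makes the stratified log-rank test in the ITT population the primary OS comparison and calls RPSFT supportive. SAP section 6 declares no change from the protocol.

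Crossover may be offered after centrally confirmed progression on regorafenib (Protocol 7.6). Neither document states the expected uptake, how patients would be selected, or how progression time relates to survival.

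**The concern.** RPSFT shrinks or stretches the time a switcher spends on the new drug, and the patient's potential censoring time moves with it. A switcher still alive at cutoff is censored on the U scale at a point that depends on when the switch happened; a non-switcher is censored at the cutoff itself. Switching follows progression, so this censoring can carry prognostic information. Re-censoring removes that dependence.

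The SAP's rule addresses the opposite situation, in which transformation lengthens survival past the cutoff. If avapritinib works, the rule as written re-censors nobody, and the point estimate itself, not only its precision, can be off. At stake is the estimate meant to show the OS effect without crossover dilution.

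**Working it through.** **The plan's own figure.** "Assuming the same effect size for OS as PFS (HR = 0.67), the same number of events (264) is required", on the basis that "a minimum of 264 PFS events are needed to provide 90% power at a 2-sided alpha of 0.05 for the study". Schoenfeld: 4 × (1.960 + 1.282)² / (ln 0.67)² = 42.03 / 0.1604 = 262.1, so 263 events. Freedman's formula gives 270. Power with 264 events is Φ(√(264/4) × 0.4005 − 1.960) = Φ(1.294) = 0.902. The 264 is sound. The documents state no RPSFT-adjusted figure to reproduce.

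**Can the rule fire?** Let C be potential follow-up from randomization to data cutoff. Observed time is T = T_off + T_on ≤ C. Then U = T − T_on × (1 − exp(psi)). If exp(psi) < 1, U ≤ T ≤ C, so U > C is impossible. It requires exp(psi) > 1, meaning that avapritinib shortens survival.

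**What is left uncorrected.** Three regorafenib patients alive at cutoff, with illustrative C = 20 months and exp(psi) = 0.67:
- crossed over at 5.5 months: censored at 5.5 + 14.5 × 0.67 = 15.2
- crossed over at 12 months: censored at 12 + 8 × 0.67 = 17.4
- never crossed over: censored at 20

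Re-censoring at min(C, C × exp(psi)) puts all three at 13.4, whatever their crossover history.

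**Inputs to the simulation.**
- From the documents: HR 0.67; "Approximately 460 patients are to be randomly assigned, in a 1:1 ratio, to 1 of 2 treatment arms"; 18-month accrual ("With an 18-month accrual period and a 6-month follow-up period"); final OS analysis at 264 deaths ("The OS will also be analyzed at the follow-up when 264 events (deaths) occur, using the remaining unspent alpha"); regorafenib median PFS 5 months (SAP 1.3); control median OS about 12 months (Protocol 1.4).
- Assumed: exponential times, uniform accrual, crossover 0.5 month after progression, and the uptake, selection and PFS-OS correlation shown.

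**Large samples** (200,000 per arm, cutoff at 264/460 deaths, true HR 0.67, 80% uptake where random). Both rules are applied to the same data, so compare within rows.

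| Correlation | Who crosses over | Rule as written | Re-censored | Difference |
|---|---|---|---|---|
| 0 | random | 0.668 | 0.669 | −0.001 |
| 0 | fitter more often | 0.644 | 0.661 | −0.017 |
| 0 | longer survivors strongly favoured | 0.664 | 0.676 | −0.012 |
| 0 | less fit more often | 0.687 | 0.672 | +0.015 |
| 0.6 | random | 0.694 | 0.669 | +0.025 |
| 0.6 | fitter more often | 0.679 | 0.668 | +0.011 |
| 0.6 | longer survivors strongly favoured | 0.693 | 0.668 | +0.025 |
| 0.6 | less fit more often | 0.690 | 0.667 | +0.023 |

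No transformed time exceeded the cutoff in any row.

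A second set (100,000 per arm, uptake 70% or 90%, with and without selection) compared the rule as written with re-censoring:
- correlation 0.3: 0.67–0.70 vs 0.66–0.68, gap 0.00 to 0.015, never away from 1
- correlation 0.6: 0.68–0.71 vs 0.66–0.68
- correlation 0.8: 0.69–0.73 vs 0.66–0.68

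The largest gap in any single run was about 0.05 to 0.07.

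**Trial size** (230 per arm, 300 trials per case, geometric means):

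| Case | ITT | As written | Re-censored | SD of log HR, as written / re-censored |
|---|---|---|---|---|
| correlation 0, random | 0.795 | 0.672 | 0.669 | 0.185 / 0.198 |
| correlation 0.6, random | 0.793 | 0.697 | 0.669 | 0.190 / 0.230 |
| correlation 0, longer survivors favoured | 0.802 | 0.663 | 0.679 | 0.225 / 0.217 |

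In the middle case the shift is ln(0.697/0.669) = 0.041, or 0.041/0.19 = 0.22 to 0.041/0.23 = 0.18 of a standard error. On the log scale, the rule as written removes ln(0.793/0.697) / ln(0.793/0.669) = 0.129/0.170, about 76%, of the dilution that re-censoring removes.

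**The case against.** **The direction is not fixed.** A reader might infer that the adjusted HR is necessarily biased toward no effect. The documents do not support that. They leave uptake, selection and the PFS-OS correlation open, and the tables show no bias, or bias away from 1, under some choices. Bias toward 1 needs early progressors to die earlier as well. That is the usual expectation in advanced cancer, but it is an assumption. The 85% crossover in Protocol 1.1.2 comes from the placebo arm of another trial and does not settle uptake here.

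**The code may be right.** The note says as appropriate and does not say only, and implementation is deferred to a paper that could not be checked. It therefore cannot be said that the programmed analysis omits re-censoring. Even so, the one circumstance the SAP names is the wrong one, and an outside reference does not turn it into a working rule.

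**The effect is small and the analysis supportive.** Both are true under the SAP. A reader might also infer that the formal OS test or its alpha spending is compromised. Under SAP 4.6.1 and 4.6.3.2 it is not, because that test is the unadjusted ITT log-rank.

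**Re-censoring costs precision.** In the correlation-0.6 case at trial size, root mean squared error of log HR is √(0.0395² + 0.190²) = 0.194 as written, where 0.0395 = ln(0.697/0.67), against about 0.230 re-censored. Removing the bias does not reduce total error there. The simulations also impose the model's own constant acceleration factor, which favours the re-censored estimate; they do not test a weaker effect after progression.

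**Conclusion.** The rule is wrong as written. It cannot trigger when exp(psi) < 1, which follows from the SAP's own formula without further assumption, and no re-censoring is stated for the psi search.

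The consequence is a possible bias in the adjusted OS HR. With a true HR of 0.67 and assumed uptake of about 70–90%, it is toward 1 by about 0.02–0.04 at correlation 0.6–0.8 (one selected case gave 0.011) and 0.00–0.015 at 0.3. It is about nil when crossover is unrelated to prognosis, and slightly away from 1 when fitter patients cross over preferentially and the correlation is zero. At trial size the shift is about one fifth of the standard error of the log HR.

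It matters little while RPSFT is supportive, as in SAP 4.6.3.2. It matters more if Protocol 10.5.3.2.2 governs, because the adjusted comparison would then be the primary analysis of a gated key secondary endpoint.

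**What to change.** Replace the note in SAP 7.4 with:

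> For each trial value of psi in the grid search and in the final adjusted comparison, all patients randomized to regorafenib (switchers and non-switchers, events and censored) are re-censored at min(C_i, C_i × exp(psi)), where C_i is the potential follow-up from randomization to data cutoff; in the grid search the same rule is applied to Arm A. Results without re-censoring are shown as a sensitivity analysis.

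When exp(psi) > 1 the minimum is C_i, so this also covers the case the present note describes. State in both documents whether RPSFT is the primary or a supportive OS comparison, and correct SAP section 6 to match.

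The cost is one SAP sentence and a few lines of code, plus some lost information. In one simulated setting with 85% uptake, Arm B deaths used fell from 140 to 123, a loss of 17. The SD of the log HR rose by 7% (0.185 to 0.198) and 21% (0.190 to 0.230) in two trial-size cases and fell by 4% (0.225 to 0.217) in the third. The adjusted confidence interval will usually be somewhat wider, which is why both results should be shown.

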### 3 STUDY ENDPOINTS

#### 3.1 Primary Endpoints

- The primary endpoint is PFS, based on central radiological assessment per mRECIST, version 1.1, in patients with advanced GIST. Progression-free survival is defined as time from randomization to disease progression, or death due to any cause, whichever occurs first.

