### **7.5.4**

## 7.6 Crossover From Regorafenib to Avapritinib

Patients who experience disease progression while receiving regorafenib (Arm B), as confirmed by central radiology review, may be offered the opportunity to cross over to the avapritinib treatment arm (Arm A).

Patients who cross over to avapritinib must complete a washout period of 7 to 28 days after their last dose of regorafenib and consent to cross over before starting treatment with avapritinib. At the first study visit after the washout period, cross over patients will complete the C1D1 assessment schedule except for the following tests, which are not required: PK blood sample and biomarker plasma sample. Otherwise patients who crossed over will follow the same schedule of assessments as on the main portion of the Protocol (except C1D15 or C2D15 visits, which are not required). After patients cross over to treatment with avapritinib, ECGs will be performed following the same schedule as prior to cross over and AEs will only be assessed for their relationship to avapritinib.

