#### *4.6.3.2 Overall Survival*

Overall survival is defined as the time from randomization to the date of death. Patients who die before or on the data cutoff date will be considered to have had an OS event. All patients who do not have a death record prior to or on the cutoff date will be censored at the last date known alive.

The primary treatment comparison will be based on a stratified log-rank test using the ITT Population. The HR and its 95% CI will be estimated using a stratified Cox model with treatment as the explanatory variable and strata as the stratification factors. An unstratified log-rank test will be performed as a sensitivity analysis.

A rank preserving structural failure time (RPSFT) model will be applied as a supportive analysis to account for treatment crossover effects from regorafenib to avapritinib. The survival time gained/lost by receiving avapritinib after crossover in the regorafenib group will be estimated. The RPSFT reconstructs the survival duration of crossover patients as if they had never received avapritinib, assuming treatment acts by multiplying survival time by a given factor once a patient starts receiving avapritinib (Korhonen et al, 2012). See Appendix 2 (Section 7.4) for further details of implementing this method.

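### SAP 7.4 names no interval or test for the RPSFT-adjusted OS result that carries the uncertainty in the estimated psi; if the usual Cox and log-rank output is used, the adjusted result looks too precise

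*SAP*

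**What the plan says.** SAP 4.6.3.2 makes the stratified log-rank test in the ITT population the primary OS comparison and adds: "The HR and its 95% CI will be estimated using a stratified Cox model with treatment as the explanatory variable". The next paragraph gives the crossover adjustment its role: "A rank preserving structural failure time (RPSFT) model will be applied as a supportive analysis". For that analysis it promises an estimate of survival time gained or lost, but no interval and no test.

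SAP 7.4 describes the steps. Psi is found by a grid search for the value at which a log-rank test of the adjusted times by randomized arm gives zero. The switchers' times are then transformed with that single value. The last step reads: "Once the transformation has been done, the data is then analyzed as usual by an appropriate method". On censoring, the section says that "censoring needs to be applied as appropriate for transformed times that extend further than the data cutoff/end of study". It closes by pointing elsewhere: "Further details of the method, and specifically the implementation in SAS, can be found in the" conference paper it cites.

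Protocol 10.5.3.2.2 discusses RPSFT and in the same section states: "The HR and its 95% CI will be estimated based on Cox's regression model with stratification factors as covariates". It does not mention psi being estimated.

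**The concern.** Psi is not known; it is estimated from the same deaths that are then analyzed. As more control patients switch, more of the control arm's adjusted survival depends on that estimate. The Cox standard error does not register this, because it is driven almost entirely by the number of deaths. An ordinary Cox interval on the adjusted times therefore treats psi as fixed and leaves out part of the sampling error, and a log-rank test on those times has the same fault.

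SAP 7.4 itself says that the conventional OS analysis can underestimate the effect after crossover, so readers will turn to the adjusted HR. If its interval is too narrow, it may look conclusive in a trial where the valid ITT test is not.

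**Working it through.** **The plan's own figure.** Both documents use 264 events for HR 0.67, 90% power and two-sided alpha 0.05. Schoenfeld: 4 × (1.960 + 1.282)² / (ln 0.67)² = 4 × 10.507 / 0.1604 = 262.1, that is 263 events. With 264 events the power is 90.2%. The figure is reproduced. With 264 deaths and 1:1 allocation the Cox SE of the log HR is about 2/√264 = 0.123, whatever the crossover rate.

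**Inputs from the documents.** 460 patients 1:1; OS cut at 264 deaths; HR 0.67; 18 months' accrual, truncated exponential with parameter -9 (protocol 10.2, SAP 1.3); control PFS median 5 months; median survival about 1 year (protocol 1.4); washout 7 to 28 days before crossover (protocol 7.6).

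**Assumptions.**
- 25, 50 or 85% of progressors switch. The only share in the documents, 85%, is the placebo arm of the earlier regorafenib trial (protocol 1.1.2).
- Accrual is weighted late. This gives 270 expected PFS events at month 24 before dropout, near the planned 264; the other direction gives 418.
- Control OS without avapritinib is exponential with median 12 months. PFS includes death (protocol 3.1), so independent progression has median 1/(1/5 − 1/12) = 8.6 months. In a second case progression is tied to OS. Control PFS is 5.0 months in both.
- The switch comes 0.5 month after progression, and time on avapritinib is stretched by 1/HR, so the RPSFT model is true.
- No dropout, unstratified, no re-censoring.

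**Method.** Estimate psi by the log-rank grid search, transform the switchers with U = T_off + T_on·exp(psi), then fit an ordinary Cox model and log-rank test. 8,000 trials per cell, Monte Carlo error at most 0.5 point. Paired entries are progression independent of OS / tied to OS.

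| Progressors switching | 25% | 50% | 85% |
|---|---|---|---|
| Control arm on avapritinib by the cut | 13/20% | 26/40% | 45/69% |
| SD of adjusted log HR, HR 0.67 | 0.133/0.133 | 0.146/0.146 | 0.173/0.173 |
| Mean Cox SE | 0.124–0.125 | 0.124–0.125 | 0.124–0.125 |
| Coverage of usual 95% CI, HR 0.67 | 93.6/93.2% | 90.6/89.9% | 84.8/80.9% |
| Null rejection, log-rank on adjusted data | 6.9/7.4% | 9.5/11.4% | 15.8/17.2% |

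The ITT log-rank rejects in 4.7–5.4% of null trials. At HR 0.67 and 85% switching, the log-rank on adjusted data is significant in 81/70% of trials and the ITT log-rank in 59/45%. With no switching, coverage is about 95% (94.3% in an 800-trial run), which isolates the estimation of psi as the cause.

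**Check by formula.** An unbiased estimate with true SD s and reported SE 0.125 has coverage 2Φ(1.96 × 0.125/s) − 1. For s = 0.133, 0.146 and 0.173 this gives 93.5, 90.7 and 84.3%, matching the independent case.

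**Bias in the tied case.** At 85% the mean adjusted HR is 0.721, a bias of ln(0.721/0.67) = 0.073. Coverage is then Φ((0.245 − 0.073)/0.173) − Φ((−0.245 − 0.073)/0.173) = 80.7%, against 84.3% without bias. So about 3.6 points of the loss are bias, not omitted uncertainty.

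**Sensitivity to control OS, PFS kept at 5 months (2,000 trials per cell).**
- Median 9 months: coverage 92–93% (50% switching) and 87–90% (85%); null rejection 8–9% and 12%.
- Median 18 months: coverage 86–87% and 72–75%; null rejection 14–15% and 26–28%.

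Uniform accrual with re-censoring, at 30, 60 and 85% switching (500 trials per cell), gave coverage of 89, 84 and 72%. The direction is stable; the size is not.

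**Alternatives at HR 0.67.** An SE of |adjusted log HR| / |ITT z| gave 95.3–96.7% coverage. The bootstrap re-estimating psi (400 trials × 200 resamples per cell, error about 1–1.3 points) gave 93.5–96.5% using its SE and 93.0–95.8% using percentiles.

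**Censoring trigger.** If psi < 0, then U = T_off + T_on·exp(psi) ≤ T_off + T_on, the observed time, which cannot pass the cutoff. So the stated trigger cannot act when avapritinib is estimated to prolong survival.

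**The case against.** The SAP does not order a wrong interval. It asks for an appropriate method and refers to an outside paper for implementation, and both documents cite a published RPSFT application; any of these may supply a valid interval. The Cox HR and CI in SAP 4.6.3.2 stand in the ITT paragraph, and the SAP promises no p-value on adjusted data. A reader might infer that the SAP prescribes an invalid CI. The text does not go that far: the step is open, and the undercoverage depends on how it is filled. That limits the point but does not remove it, since the inference method is not fixed in advance and the only OS methods the documents name treat psi as known.

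A reader might also infer that the OS type I error is at stake, because protocol 10.5.3.2.2 makes RPSFT the primary OS comparison. SAP 4.6.3.2 makes it supportive and gives the primary comparison to the ITT stratified log-rank test, so under the SAP the gatekept test is sound. The disagreement between the documents, and the SAP section 6 statement that nothing changed, need separate reconciliation and add no weight here.

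The 85% figure is not a forecast: it comes from placebo patients in another trial, and here crossover from an active control is optional. At 25% the loss is small.

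**Conclusion.** The point holds as an unspecified step with a foreseeable error, and is worth correcting before the OS analysis. If the ordinary Cox and log-rank output is used, the shortfall in coverage is one to two points at 25% switching, about four to five at 50%, and about ten with independent progression at 85%. The 81% in the tied case should not be charged wholly to psi, because part of it is bias in the adjusted HR. These sizes rest on assumed crossover rates, exponential control OS with a 12-month median, a true RPSFT model and an unstratified analysis.

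Confidence is high that the ordinary interval is wrong if used, and medium that it would be used. No gatekept decision changes. What changes is how precise the crossover-adjusted HR appears.

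The censoring trigger is a minor matter. A reader might infer that re-censoring would improve the analysis; the results do not show that overall. In the tied case at 85% it moves the mean HR from 0.721 to 0.675, but the root mean squared error of the log HR rises from 0.188 to 0.219.

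**What to change.** In SAP 7.4, replace the last analysis step with the following:

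- Take the 95% CI for the adjusted HR from a bootstrap that resamples within arm and re-estimates psi in every resample. Use the SE |adjusted log HR| / |ITT z| as a check when z is not near 0.
- Show the stratified ITT log-rank p-value beside the adjusted HR, and do not test the adjusted data.
- Optional: add a re-censored sensitivity analysis, and state in advance whether it or the unre-censored result leads.

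The cost is a few sentences, some bootstrap programming and a wider interval. The bootstrap SE is about 0.135, 0.147 and 0.175 at 25, 50 and 85% switching, instead of about 0.125. For an adjusted HR of 0.67, exp(ln 0.67 ± 1.96 × SE) moves the 95% CI from 0.52–0.86 to 0.51–0.87, 0.50–0.89 and 0.48–0.94. With the optional analysis two adjusted HRs are shown, the re-censored one noisier.
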